**An SAE is defined as any untoward medical occurrence that, at any dose, meets 1 or more of the criteria listed below:**

**a. Results in death**

**b. Is life-threatening**

The term "life threatening" in the definition of "serious" refers to an event in which the participant was at risk of death at the time of the event. It does not refer to an event that hypothetically might have caused death if it were more severe.

**c. Requires inpatient hospitalization or prolongation of existing hospitalization**

In general, hospitalization signifies that the participant has been detained (usually involving at least an overnight stay) at the hospital or emergency ward for observation and/or treatment that would not have been appropriate in the physician's office or

outpatient setting. Complications that occur during hospitalization are AEs. If a complication prolongs hospitalization or fulfills any other serious criteria, the event is serious. When in doubt as to whether “hospitalization” occurred or was necessary, the AE should be considered serious.

Hospitalization for elective treatment of a preexisting condition that did not worsen from baseline is not considered an AE.

**d. Results in persistent or significant disability/incapacity**

- The term disability means a substantial disruption of a person's ability to conduct normal life functions.
- This definition is not intended to include experiences of relatively minor medical significance, such as uncomplicated headache, nausea, vomiting, diarrhea, influenza, and accidental trauma (eg, sprained ankle), that may interfere with or prevent everyday life functions but do not constitute a substantial disruption.

**e. Is a congenital anomaly/birth defect**

**f. Is a suspected transmission via a Pfizer product of an infectious agent, pathogenic or non-pathogenic.**

The event may be suspected from clinical symptoms or laboratory findings indicating an infection in a participant exposed to a Pfizer product. The terms “suspected transmission” and “transmission” are considered synonymous. These cases are considered unexpected and handled as serious expedited cases by pharmacovigilance personnel. Such cases are also considered for reporting as product defects, if appropriate.

**g. Other situations:**

- Medical or scientific judgment should be exercised by the investigator in deciding whether SAE reporting is appropriate in other situations, such as significant medical events that may jeopardize the participant or may require medical or surgical intervention to prevent one of the other outcomes listed in the above definition. These events should usually be considered serious.
- Examples of such events include invasive or malignant cancers, intensive treatment in an emergency room or at home for allergic bronchospasm, blood dyscrasias or convulsions that do not result in hospitalization, or development of drug dependency or drug abuse.
- Progression of the malignancy under study (including signs and symptoms of progression) should not be reported as an SAE unless the outcome is fatal within the active collection period. Hospitalization due to signs and symptoms of disease progression should not be reported as an SAE. If the malignancy has a fatal outcome during the study, the event leading to death must be recorded as an

AE on the CRF, and as an SAE with CTCAE Grade 5 (see the [Assessment of Intensity](#) section) if it occurs during the active collection period.

### 10.3.3. Recording/Reporting and Follow-up of AEs and/or SAEs During the Active Collection Period

#### AE and SAE Recording/Reporting

The table below summarizes the requirements for recording AEs on the CRF and for reporting SAEs on CT SAE Report Form to Pfizer Safety throughout the active collection period. These requirements are delineated for 3 types of events: (1) SAEs; (2) nonserious AEs; and (3) exposure to the study intervention under study during pregnancy or breastfeeding, and occupational exposure.

It should be noted that the CT SAE Report Form for reporting SAE information is not the same as the AE page of the CRF. When the same data is collected, the forms must be completed in a consistent manner. AEs should be recorded using concise medical terminology and the same AE term should be used on both the CRF and the CT SAE Report Form for reporting of SAE information.

Safety Event	Recorded on the CRF	Reported on the CT SAE Report Form to Pfizer Safety Within 24 Hours of Awareness
SAE	All	All
Nonserious AE	All	None
Exposure to the study intervention under study during pregnancy or breastfeeding	All AEs/SAEs associated with EDP or EDB  Note: Instances of EDP or EDB not associated with an AE or SAE are not captured in the CRF	All instances of EDP are reported (whether or not there is an associated SAE)*  All instances of EDB are reported (whether or not there is an associated SAE) **
Environmental or occupational exposure to the product under study to a non-participant (not involving EDP or EDB)	None. Exposure to a study non-participant is not collected on the CRF	The exposure (whether or not there is an associated AE or SAE) must be reported***

\* EDP (with or without an associated AE or SAE): any pregnancy information is reported to Pfizer Safety using the CT SAE Report Form and EDP Supplemental Form; if the EDP is associated with an SAE, then the SAE is reported to Pfizer Safety using the CT SAE Report Form.

\*\*EDB is reported to Pfizer Safety using the CT SAE Report Form, which would also include details of any SAE that might be associated with the EDB.

\*\*\*Environmental or occupational exposure: AEs or SAEs associated with occupational exposure are reported to Pfizer Safety using the CT SAE Report Form.

- When an AE/SAE occurs, it is the responsibility of the investigator to review all documentation (eg, hospital progress notes, laboratory reports, and diagnostic reports) related to the event.
- The investigator will then record all relevant AE/SAE information in the CRF.
- It is not acceptable for the investigator to send photocopies of the participant's medical records to Pfizer Safety in lieu of completion of the CT SAE Report Form/AE/SAE CRF page.
- There may be instances when copies of medical records for certain cases are requested by Pfizer Safety. In this case, all participant identifiers, with the exception of the participant number, will be redacted on the copies of the medical records before submission to Pfizer Safety.
- The investigator will attempt to establish a diagnosis of the event based on signs, symptoms, and/or other clinical information. Whenever possible, the diagnosis (not the individual signs/symptoms) will be documented as the AE/SAE.

#### Assessment of Intensity

The investigator will make an assessment of intensity for each AE and SAE reported during the study and grade it according to the NCI-CTCAE (Version 5.0)

GRADE	Clinical Description of Severity
1	MILD adverse event
2	MODERATE adverse event
3	SEVERE adverse event
4	LIFE-THREATENING consequences; urgent intervention indicated
5	DEATH RELATED TO adverse event

#### Assessment of Causality

- The investigator is obligated to assess the relationship between study intervention and each occurrence of each AE/SAE. The investigator will use clinical judgment to determine the relationship.

- A “reasonable possibility” of a relationship conveys that there are facts, evidence, and/or arguments to suggest a causal relationship, rather than a relationship cannot be ruled out.
- Alternative causes, such as underlying disease(s), concomitant therapy, and other risk factors, as well as the temporal relationship of the event to study intervention administration, will be considered and investigated.
- The investigator will also consult the SRSD(s) and/or product information, for marketed products, in his/her assessment.
- For each AE/SAE, the investigator **must** document in the medical notes that he/she has reviewed the AE/SAE and has provided an assessment of causality.
- There may be situations in which an SAE has occurred and the investigator has minimal information to include in the initial report to the sponsor. However, **it is very important that the investigator always make an assessment of causality for every event before the initial transmission of the SAE data to the sponsor.**
- The investigator may change his/her opinion of causality in light of follow-up information and send an SAE follow-up report with the updated causality assessment.
- The causality assessment is one of the criteria used when determining regulatory reporting requirements.
- If the investigator does not know whether or not the investigational product caused the event, then the event will be handled as “related to investigational product” for reporting purposes, as defined by the sponsor. In addition, if the investigator determines that an SAE is associated with study procedures, the investigator must record this causal relationship in the source documents and CRF, and report such an assessment in the dedicated section of the CT SAE Report Form and in accordance with the SAE reporting requirements.

#### Follow-up of AEs and SAEs

- The investigator is obligated to perform or arrange for the conduct of supplemental measurements and/or evaluations, as medically indicated or as requested by the sponsor, to elucidate the nature and/or causality of the AE or SAE as fully as possible. This may include additional laboratory tests or investigations, histopathological examinations, or consultation with other healthcare providers.

- New or updated information will be recorded in the originally submitted documents.
- The investigator will submit any updated SAE data to the sponsor within 24 hours of receipt of the information.

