##### **8.4.1. Time Period and Frequency for Collecting AE and SAE Information**

The time period for actively eliciting and collecting AEs and SAEs (“active collection period”) for each participant begins from the time the participant provides informed consent, which is obtained before undergoing any study related procedure and/or receiving study intervention, through and including a minimum of 9 weeks after the last administration of the study intervention, except as indicated below, after the last administration of the study intervention.

For participants who are screen failures, the active collection period ends when screen failure status is determined.

The “active collection period” for VOD/SOS is the entire duration of study participation, including the long term follow-up period, regardless of whether new anti-cancer treatment is initiated. All cases of VOD/SOS will be reported in the CRF for up to 2 years from Cycle 1 Day 1 and must be reported as SAEs (recorded on the CRF and CT SAE Report Form).

Follow-up by -the investigator continues throughout the active collection period and until the AE or SAE or its sequelae resolve or stabilize at a level acceptable to the investigator.

When a clinically important AE remains ongoing at the end of the active collection period, follow-up by the investigator continues until the AE or SAE or its sequelae resolve or stabilize at a level acceptable to the investigator and Pfizer concurs with that assessment.

If the participant withdraws from the study and also withdraws consent for the collection of future information, the active collection period ends when consent is withdrawn.

If a participant permanently discontinues or temporarily discontinues study intervention because of an AE or SAE, the AE or SAE must be recorded on the CRF and the SAE reported using the CT SAE Report Form.

Investigators are not obligated to actively seek information on AEs or SAEs after the participant has concluded study participation. However, if the investigator learns of any SAE, including a death, at any time after a participant has completed the study, and they consider the event to be reasonably related to the study intervention, the investigator must promptly report the SAE to Pfizer using the CT SAE Report Form.

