#### Events Meeting the AE Definition

- Any abnormal laboratory test results (hematology, clinical chemistry, or urinalysis) or other safety assessments (eg, ECG, radiological scans, vital sign measurements), including those that worsen from baseline, considered clinically significant in the medical and scientific judgment of the investigator. Any abnormal laboratory test results that meet any of the conditions below must be recorded as an AE:
  - Is associated with accompanying symptoms;
  - Requires additional diagnostic testing or medical/surgical intervention;
  - Leads to a change in study dosing (outside of any protocol-specified dose adjustments) or discontinuation from the study, significant additional concomitant drug treatment, or other therapy.
- Exacerbation of a chronic or intermittent preexisting condition, including an increase in either frequency and/or intensity of the condition.
- New conditions detected or diagnosed after study intervention administration, even though it may have been present before the start of the study.
- Signs, symptoms, or the clinical sequelae of a suspected drug-drug interaction.
- Signs, symptoms, or the clinical sequelae of a suspected overdose of either study intervention or a concomitant medication. Overdose per se will not be reported as an AE/SAE unless it is an intentional overdose taken with possible suicidal/self-harming intent. Such overdoses should be reported regardless of sequelae.

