3.5. Safety Endpoints

Safety endpoints will be summarized based on the on-treatment period unless otherwise specified.

On-treatment is defined as the time from the first dose of study treatment through minimum (9 weeks after the last administration of the investigational product, start day of new anti-cancer therapy – 1 day). The start date of new anti-cancer therapy after the first dose of study treatment is derived as outlined in [Section 5.2.5](#). Adverse events occurring on the same day as the first dose of study treatment will be considered to have occurred during the on-treatment period. All other assessments which occur on the same day as the first dose of study treatment will be considered baseline assessments (see [Section 3.4](#) for the definition of baseline). If the exact time is collected, the last assessment before the time of first dose of study treatment will be considered as baseline assessments.

Safety data collected outside the on-treatment period as described above will be listed but not summarized.

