3.5.1. Adverse Events

Adverse events (AEs) will be coded to preferred term (PT) and system organ class (SOC) using the Medical Dictionary for Regulatory Activities (MedDRA) and classified by severity using the National Cancer Institutes (NCI) Common Terminology Criteria for Adverse Events (CTCAE), version 5.0. For other AEs without specific NCI CTCAE v5.0 definitions, results will be identified according to NCI CTCAE v5.0 “other” categories.

An event will be considered treatment related if the investigator considers so.

An adverse event is considered treatment-emergent relative to a given treatment if the event start date is during the on-treatment period (including on the date of first dose). All cases of VOD/SOS irrespective of causality or severity will be reported as SAEs for up to 2 years after the first dose of inotuzumab ozogamicin.

Adverse Events of Special Interest (AESI)

AEs of special interest (AESI) are as follows:

- GRADE ≥ 3 HEPATOTOXICITY AND/OR SERIOUS HEPATOTOXICITY, INCLUDING VOD/SOS;
- MYELOSUPPRESSION/CYTOPENIA;
- INTERSTITIAL LUNG DISEASE;
- INFLAMMATORY GASTROINTESTINAL EVENT;
- PANCREATITIS;
- SECONDARY PRIMARY MALIGNANCY;

- REPRODUCTIVE AND DEVELOPMENT TOXICITY;
- NEPHROTOXICITY; and
- NEUROTOXICITY.

These events are defined in [Appendix 2](#).

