6.6.1. Adverse Events

All analyses will be based on treatment emergent events unless otherwise specified. Treatment emergent is defined in [Section 3.5.1](#). AEs not considered treatment emergent will be flagged in data listings.

A high level summary of TEAEs (all causality), TEAEs (treatment related) and Cycle 1 TEAEs (treatment related) will include the number and percentage of participants with:

- Any TEAE;
- Serious TEAE;
- TEAE with CTCAE Grade 3-4;
- Grade 5 TEAE;

- TEAEs leading to dose reductions of inotuzumab ozogamicin;
- TEAEs leading to dose delay of inotuzumab ozogamicin;
- TEAEs leading to permanent discontinuation of inotuzumab ozogamicin.

Additionally, the number of events reported for each of the categories above will be provided. Each unique adverse event at the PT level for a participant is included in the count.

Seriousness, toxicity grade, action taken (interruption, reduction, and withdraw) are as reported by the investigator on the adverse event CRF.

Summaries of TEAE by SOC and PT in decreasing frequency will be provided for:

- TEAEs (All Causality);
- TEAEs by Maximum Toxicity Grade (All Causality);
- TEAEs (Treatment related);
- TEAEs by maximum toxicity grade (Treatment related);
- Serious TEAEs (All causality);
- Post-HSCT SAE (All causality);
- Serious TEAEs (Treatment related); and
- Post-HSCT SAE (Treatment related).

An event will be considered treatment related if the investigator considers so.

The following summaries will be provided by PT only (ie, summaries will not include SOC) in decreasing frequency:

- TEAEs (All causality);
- TEAEs (All causality) experienced by $\geq 10\%$ of participants;
- TEAEs (All causality) by maximum toxicity grade;
- Grade 3-5 TEAEs (All causality and Treatment related);
- TEAEs leading to dose delays of inotuzumab ozogamicin (all causality);
- TEAEs leading to dose reductions of inotuzumab ozogamicin (all causality);

- TEAEs leading to permanent discontinuation of inotuzumab ozogamicin (all causality);
- Serious TEAEs (all causality); and
- Post-HSCT SAEs (all causality).

Each participant will be counted only once within each SOC and PT.

As described in [Section 5.3](#), in case a participant has events with missing and/or non missing toxicity grades, the maximum of the non-missing grade will be displayed. Missing grade will only be displayed in the event that only one event has been reported for a participant and the grade is missing.

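### SAP 3.5.1 decides treatment-emergence by start date alone, so an AE open at first dose that worsens on drug may be left out of the TEAE tables, depending on how it is recorded

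*Protocol*

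**What the plan says.** **Collection.** Protocol 8.4.1 states that active AE collection "begins from the time the participant provides informed consent".

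**Updates.** Protocol 10.3.3, under follow-up of AEs and SAEs, states: "New or updated information will be recorded in the originally submitted documents".

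**Worsening as an AE.** Protocol 10.3.1 lists among events that meet the AE definition: "Exacerbation of a chronic or intermittent preexisting condition, including an increase in either frequency and/or intensity of the condition". The same list includes clinically significant laboratory abnormalities, among them values that get worse relative to baseline.

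**Treatment-emergence.** SAP 3.5.1 states: "An adverse event is considered treatment-emergent relative to a given treatment if the event start date is during the on-treatment period". SAP 3.5 sets the start of that period: "On-treatment is defined as the time from the first dose of study treatment through minimum" the earlier of 9 weeks after the last dose and the day before new anti-cancer therapy.

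**Scope of the tables.** SAP 6.6.1 bases AE analyses on treatment-emergent events by default and adds: "AEs not considered treatment emergent will be flagged in data listings". SAP 3.5 states: "Safety data collected outside the on-treatment period as described above will be listed but not summarized".

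**CRF practice.** Protocol 10.1.7 leaves CRF completion rules to a separate document, which is not part of the protocol or SAP.

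**The concern.** A start-date rule works when every clinically relevant change on drug has its own onset date. It fails when an event opens between consent and first dose at a low grade and becomes Grade 3-4 or serious after dosing within the same record. Such an event happens on treatment but is classified as pre-treatment.

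In this study the AE tables are the main summary of clinical toxicity: infection, haemorrhage, neurotoxicity and lung events have no other one. Infection and haemorrhage are grouped in SAP Appendix 2 as complications of myelosuppression. The study is a post-approval commitment to confirm safety, among other aims, in about 44 patients, so one uncounted patient is visible in a preferred-term rate.

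**Working it through.** The plan states no figure for this point, so there is none to reproduce. The check follows one event through the rules.

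**1. Can an AE record be open before first dose?** Yes. Collection starts at consent (Protocol 8.4.1). Screening runs up to 28 days before enrollment, and treatment normally starts within 3 days of enrollment (Protocol 1.3, Table 1 and its footnotes 12 and 17). If consent is signed at the start of screening, the window is 28 + 3 = 31 days. It is shorter when standard-of-care tests done before consent serve as screening tests, as footnote 17 allows. It can be longer if the sponsor permits a later start.

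**2. How is a worsening of that open AE recorded?** The documents leave two routes.

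| Route | Start date of the record | SAP 3.5.1 | TEAE tables |
|---|---|---|---|
| A. Update to the open record (one reading of Protocol 10.3.3) | Before first dose | Not treatment-emergent | Omitted, flagged in a listing |
| B. New AE for the worsening (one reading of Protocol 10.3.1) | On treatment | Treatment-emergent | Counted |

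The follow-up bullet in Protocol 10.3.3 mentions neither grade nor onset date. The exacerbation bullet in Protocol 10.3.1 says what counts as an AE, not whether an AE already on the CRF gets a second record. The deciding instruction would be in the CRF completion document.

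**3. Does the SAP rescue route A elsewhere?** No clause in SAP 3.5.1 or 6.6.1 does so. SAP 5.3.3.1 allows for repeated similar events in one participant, but only to govern date imputation. That section also creates an asymmetry: a unique or first event with a missing onset date and a stop date after first dose is given the first-dose date and is counted, while a documented pre-dose onset with worsening on drug is not.

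**4. Is the AESI summary affected?** Probably. SAP 6.6.1.1 gives no exemption from the default in 6.6.1. However, the term lists in SAP Appendix 2 carry no treatment-emergence condition, so the documents do not settle it.

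**5. What is covered elsewhere?** Laboratory grade shifts, including from Grade 2 or lower to Grade 3 or higher, and liver-test thresholds (SAP 6.6.3); deaths (SAP 6.6.2); VOD/SOS, which has its own summary if data permit (SAP 6.6.1.1).

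**6. Size.** With k patients missed in the same table row, the rate falls by k/44: 1/44 = 2.3 points, 2/44 = 4.5 points, 3/44 = 6.8 points. The documents give no basis for choosing k. Patients missed for different terms fall in different rows. A patient missed for one term may still be counted in the any-Grade-3-4 or any-serious row through another event.

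**The case against.** The strongest reply is that the protocol already treats worsening as an AE in its own right. Protocol 10.3.1 covers exacerbation of preexisting conditions and clinically significant laboratory worsening relative to baseline. Its exclusions remove day-to-day fluctuation only where there is no worsening. Protocol 10.3.3 asks for a causality assessment of each occurrence. A site that reads these together would open a new record, and the event would be counted.

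This stands for conditions in the medical history and for baseline laboratory values that were never entered as AEs. It narrows the gap to AEs opened between consent and first dose. It does not close the gap, because none of these texts says that an AE already open gets a new record and date when its grade rises.

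A reader might go further and infer that Protocol 10.3.3 forces updating in place, so that such events can never reach the TEAE tables. The text does not support that: it is a general instruction on where follow-up information goes.

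A reader might also point to the liver values allowed by inclusion criterion 7, or the low counts foreseen in redosing criterion 8, as proof that many patients are affected. Those are permitted baseline values, not open AEs. Under Protocol 8.3.4 and 10.3.1, abnormalities associated with the leukemia are generally not AEs unless more severe than expected. Exclusion criteria 14 and 18 further limit what can be open at entry.

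It is also true that laboratory worsening, deaths and VOD/SOS have their own summaries. They do not cover other clinical events, and the laboratory tables carry no seriousness, relatedness or action taken.

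**Conclusion.** The point holds as a gap in the rule. For an AE opened between consent and first dose that worsens on drug, SAP 3.5.1 as written gives a count that depends on an unstated data-entry convention. Under route A the event is omitted from the TEAE tables and probably from the AESI summary; under route B it is counted. Any error is an undercount.

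The size per patient is 2.3 points, assuming 44 treated patients. The total cannot be derived, because the documents do not say how many AEs will be open at first dose, how many will worsen, or how sites will record them. A claim that the TEAE rates are biased low by a given amount would therefore go beyond the documents. The point merits correction because the present rule gives a wrong count under one permissible practice, and the corrected rule counts such a worsening whichever way it is entered, provided its grade or seriousness is dated.

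**What to change.** 1. **SAP 3.5.1.** Add that an AE with onset before first dose is also treatment-emergent if, during the on-treatment period, it increases in CTCAE grade over its pre-dose grade or becomes serious. Participants would not be double-counted, because SAP 6.6.1 counts each once per system organ class and preferred term.
2. **CRF instructions.** Record such a worsening as a new record, dated at the change and linked to the first, and align Protocol 10.3.3 with this.
3. **Data already entered.** Review AEs open at first dose and apply the new clause where a dated grade or seriousness is available. Where an update has overwritten the earlier grade, the pre-dose grade may not be recoverable; the documents do not show that dated changes are kept.
4. **SAP 6.6.1.1.** State whether the AESI summary is limited to TEAEs.

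The cost is one SAP sentence, one CRF instruction, a small record review and slightly higher TEAE counts.
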